Lenvatinib should be withheld in any instances where a subject is at imminent risk to develop a hypertensive crisis or has significant risk factors for severe complications of uncontrolled hypertension (eg, BP  $\geq$ 99th percentile [BP  $\geq$ 160/100 mm Hg], significant risk factors for cardiac disease, intracerebral hemorrhage, or other significant comorbidities). Once the

subject has been on the same antihypertensive medications for at least 48 hours and the BP is controlled, lenvatinib should be resumed as described below.

During the Treatment Period, subjects with systolic BP  $\geq$ 99th percentile (BP  $\geq$ 160 mm Hg) or diastolic BP  $\geq$ 99th percentile (BP  $\geq$ 100 mm Hg) must have their BP monitored on Day 15 (or more frequently as clinically indicated) until systolic BP has been  $<$ 95th percentile ( $\leq$ 150 mm Hg) and diastolic BP has been  $<$ 95th percentile ( $\leq$ 95 mm Hg) for 2 consecutive treatment cycles. If a repeat event of systolic BP  $\geq$ 99th percentile (BP  $\geq$ 160 mm Hg) or diastolic BP  $\geq$ 99th percentile (BP  $\geq$ 100 mm Hg) occurs, the subject must resume the Day 15 evaluation until systolic BP has been  $<$ 95th percentile ( $\leq$ 150 mm Hg) and diastolic BP has been  $<$ 95th percentile ( $\leq$ 95 mm Hg) for 2 consecutive treatment cycles.

The following guidelines should be followed for the management of systolic BP  $\geq$ 99th percentile (BP  $\geq$ 160 mm Hg) or diastolic BP  $\geq$ 99th percentile (BP  $\geq$ 100 mm Hg) confirmed on repeat measurements after at least 30 minutes:

[figure not shown]
- Continue lenvatinib and institute antihypertensive therapy for subjects not already receiving this.
- For those subjects already on antihypertensive medication, the dose of the current agent may be increased, if appropriate, or 1 or more agents of a different class of antihypertensive should be added.
- If systolic BP  $\geq$ 99th percentile (BP  $\geq$ 160 mm Hg) or diastolic BP  $\geq$ 99th percentile (BP  $\geq$ 100 mm Hg) persists despite maximal antihypertensive therapy, then lenvatinib administration should be interrupted and restarted at a lower dose QD (one dose level reduction [20%]) only when systolic BP  $<$ 95th percentile (BP  $\leq$ 150 mm Hg) and diastolic BP  $<$ 95th percentile (BP  $\leq$ 95 mm Hg) and the subject has been on a stable dose of antihypertensive medication for at least 48 hours.

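### Section 8.4.1.1.2 gives opposite lenvatinib instructions for a subject whose systolic and diastolic pressures are both confirmed at or above the 99th percentile (160/100 mm Hg) and who has no other risk factor

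*Protocol*

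**What the plan says.** All of this is in Protocol section 8.4.1.1.2, which appears twice in the protocol file with the same thresholds and instructions.

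- **Withhold sentence.** "Lenvatinib should be withheld in any instances where a subject is at imminent risk to develop a hypertensive crisis". The same sentence extends this to subjects with important risk factors for serious harm from hypertension that is not under control. Its bracket lists these examples: "eg, BP $\geq$ 99th percentile [BP $\geq$ 160/100 mm Hg], significant risk factors for cardiac disease, intracerebral hemorrhage, or other significant comorbidities". The condition for resuming comes next: "subject has been on the same antihypertensive medications for at least 48 hours and the BP is controlled, lenvatinib should be resumed as described below".
- **Bullet list.** It opens with "The following guidelines should be followed for the management of systolic BP" at or above the 99th percentile (160 mm Hg), or diastolic pressure at or above the 99th percentile (100 mm Hg), confirmed after at least 30 minutes. The first bullet is "Continue lenvatinib and institute antihypertensive therapy for subjects not already receiving this". The second covers subjects already treated and escalates their antihypertensives. Only the third stops lenvatinib: if pressure at that level "persists despite maximal antihypertensive therapy, then lenvatinib administration should be interrupted and restarted at a lower dose QD".

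Two other places bear on the order of actions. Table 1 footnote b asks for optimal medical management of hypertension, among other toxicities, before any interruption or dose reduction. The opening of 8.4.1.1.2 says that early detection and management should limit the need for interruptions and reductions.

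**The concern.** The same pressure limits appear in two instructions that point in opposite directions, and nothing states which prevails. Hypertension is a recognised effect of this drug class, as the section itself says, and the rule applies to a largely young population: at least 32 of about 72 randomised subjects must be under 18. For them the 99th percentile lies well below 160/100. In Appendix 6 it is 121/82 mm Hg for a 6-year-old boy at median height and 127/88 at age 10.

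Two consequences follow if sites differ in which sentence they apply. First, a dose reduction is close to permanent: section 8.4.1.1 does not allow a reduced dose to be raised again unless the reduction was a mistake and the sponsor agrees. A site that withholds at first detection and then borrows the restart rule from the bullets could fix a lower dose for the rest of treatment. Second, section 8.7.1.8.1 reports interruptions, reductions and discontinuations due to adverse events. In Arm A these counts would partly reflect the sentence a site chose.

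**Working it through.** The protocol states no figure on this point, so there is none to reproduce. The check compares the trigger and the action of each rule.

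| | Withhold sentence | Bullet list |
|---|---|---|
| Trigger | Imminent risk of crisis, or significant risk factors; pressure at or above the 99th percentile [160/100] is the first example and is not tied to another factor | Systolic at or above the 99th percentile (160) **or** diastolic at or above the 99th percentile (100) |
| Confirmation | None stated | After at least 30 minutes |
| Action | Withhold | Continue and treat |
| Interruption | At once | Only if the elevation persists despite maximal therapy |
| Restart | At least 48 hours on the same medication and pressure controlled; dose as described below | One dose level lower (20%) after persistence; a further level for each recurrence after a reduction |

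Applied to cases:

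1. **Both components confirmed above the limits, no antihypertensives yet, no other risk factor** (for example 165/105 in an adult). The withhold sentence applies through its first example. The first bullet also applies. One says withhold, the other says continue. This is a direct contradiction.
2. **Same pressure, not yet confirmed.** Only the withhold sentence speaks. The 30-minute step separates the rules until confirmation, then case 1 applies.
3. **Only one component above its limit, confirmed.** The bullets apply. Whether the withhold example applies is unclear, because 160/100 is written without saying whether either component suffices.
4. **Pressure above the limits plus a further listed risk factor.** The sentence says withhold. The bullets have no exception for this case, and no precedence is stated.

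Next, the restart dose. The withhold sentence refers the reader to the text below. That text gives restart doses only for pressure that persists despite maximal therapy, or that recurs after a first or second dose reduction. A subject withheld at first detection fits none of these, so no restart dose is given.

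Last, the size. The introduction (6.3.1) reports hypertension in 36% of 31 subjects on single-agent lenvatinib. Applied to Arm A this is 0.36 × 36 = 12.96, about 13 subjects with hypertension of any degree. To count subjects facing case 1, that must be multiplied by the share who reach the 99th percentile in both components. No such share is given. For the combination cohort the introduction does not name hypertension among the most frequent events and gives no rate for it.

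**The case against.** The strongest defence is that the protocol does indicate an order: medical management first, interruption later. Table 1 footnote b says so, the section's opening is consistent with it, and the bullets follow it. On this view the withhold sentence is a risk override on a stepwise algorithm. It turns on clinical judgement of imminent crisis or severe complications, and the pressure level is one illustration beside cardiac risk, intracerebral hemorrhage and comorbidities. Its 48-hour condition matches the one in the interruption bullets, which suggests that it may simply anticipate them.

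Much of this stands as a likely intention. It does not settle the text. The pressure level is listed as an example of the risk by itself, not joined to another factor, so the override reading has to be supplied by the reader. Footnote b asks that management be started before interruption; a site that starts an antihypertensive and then withholds lenvatinib could claim to have met it. Section 8.4.1.1 also sends sites to the subsections before Table 1, so the footnote is not placed above them.

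The objection does limit the point in three ways. A reader might infer that the safety rule cannot be followed at all; that goes too far, because the bullets and footnote b form a usable sequence and the contradiction is certain only in case 1. A reader might infer that any reading at this level triggers opposite actions; before confirmation, or with one component raised, the documents do not show that. And Figure 2, which sets out the hypertension procedure, is not shown in the text available here. Sites have it and it may clarify the sequence, although it would not remove the conflicting wording.

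**Conclusion.** The contradiction is real and narrow. For a subject with both components confirmed at or above the limits and no other risk factor, 8.4.1.1.2 says both withhold and continue, and a subject withheld at first detection has no stated restart dose. This rests on the wording alone and assumes nothing about Figure 2.

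The number of subjects affected cannot be derived. A reader might take 13 of 36 Arm A subjects as the size; that figure counts hypertension of any degree and assumes that the single-agent rate carries over to the combination. A reader might also infer that most sites treat a single subject. About 72 subjects at about 70 sites give a mean of 72/70 ≈ 1.03, which says nothing about the distribution.

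This is an internal inconsistency in a safety and dosing instruction, not a flaw in the statistical design. The sample size and the primary test of PFS-4m are unaffected. What may be affected is the consistency of handling across sites and the meaning of the Arm A interruption and reduction counts.

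**What to change.** The clinical team should reconcile four items: the withhold sentence and its pressure example, the bullets for confirmed pressure at or above the 99th percentile, Table 1 footnote b, and Figure 2. The reconciled text should:

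- lead from each confirmed pressure level and risk state to one stated action;
- say whether the limits apply to either component or to both;
- say whether confirmation is needed before the withhold instruction applies;
- give one restart rule, including the dose, for every route by which lenvatinib can be stopped for hypertension.

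This review takes no position on which action or dose is right. The cost is a clarified paragraph, with Figure 2 and footnote b aligned to it, in the next amendment. No change to the sample size or the analysis is needed.

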**Figure 2      Management of Hypertension**

BP = blood pressure, HTN = hypertension, Tx = treatment.

#### 8.4.1.1.3 MANAGEMENT OF POSTERIOR REVERSIBLE LEUKOENCEPHALOPATHY SYNDROME/REVERSIBLE POSTERIOR LEUKOENCEPHALOPATHY SYNDROME

Posterior Reversible Leukoencephalopathy Syndrome (PRES)/Reversible Posterior Leukoencephalopathy Syndrome (RPLS) is a neurological disorder that can present with headache, seizure, lethargy, confusion, altered mental function, blindness, and other visual or neurological disturbances. Mild to severe hypertension may be present. An MRI is

necessary to confirm the diagnosis of PRES/RPLS. Appropriate measures should be taken to control BP (see [Section 8.4.1.1.1](#) and [8.4.1.1.2](#)), and neurologic consultation is advised. In subjects with signs or symptoms of PRES/RPLS, dose modification guidelines as per [Table 1](#) should be followed.

#### 8.4.1.1.4 MANAGEMENT OF PROTEINURIA

Regular assessment for proteinuria should be conducted as detailed in the Schedule of Assessments ([Table 5](#) and [Table 6](#)). Guidelines for assessment and management of proteinuria are summarized as follows:

##### Grading of Proteinuria

- Grading according to CTCAE 5.0 ([Cancer Therapy Evaluation Program, 2017](#)) will be based on the protein-creatinine ratio or 24-hour urinary protein result, if available. For subjects  $\geq 18$  years of age, if the subject has 4+ proteinuria by dipstick, a 24-hour urinary protein result is required to confirm Grade 3 proteinuria.

##### Management of Proteinuria

- Management of lenvatinib administration will be based on the grade of proteinuria according to [Table 1](#).
- In the event of nephrotic syndrome, lenvatinib must be discontinued.

##### Detection and Confirmation

- Perform urine dipstick testing per the Schedule of Assessments ([Table 5](#) and [Table 6](#))
- For subjects  $\geq 18$  years of age, a 24-hour urine collection initiated as soon as possible and at least within 72 hours (or an immediate spot urine protein-to-creatinine ratio [UPCR] test) AND for subjects  $< 18$  years of age, an immediate spot UPCR test, and if possible, a 24-hour urine collection (initiated as soon as possible and at least within 72 hours) is required in the following situations:
  - The first (initial) occurrence of  $\geq 2+$  proteinuria on urine dipstick while on lenvatinib
  - A subsequent increase in severity of urine dipstick proteinuria occurring on the same lenvatinib dose level
  - When there has been a lenvatinib dose reduction and at the new dose level the urine protein dipstick result is  $\geq 2+$
- For subjects  $\geq 18$  years of age, a 24-hour urine collection (initiated as soon as possible and at least within 72 hours) to verify the grade of proteinuria is required when UPCR is  $\geq 2.4$ .

##### Monitoring

- Urine dipstick testing for subjects with proteinuria  $\geq 2+$  should be performed on Day 15 (or more frequently as clinically indicated) until the results have been 1+ or negative for 2 consecutive treatment cycles.

- Proteinuria monitoring can be performed at the local laboratory or investigator site, but must be managed by the site physician.

#### 8.4.1.1.5 MANAGEMENT OF HEPATOTOXICITY

Regular monitoring of liver function tests (ALT, AST, bilirubin levels) should be conducted as detailed in the Schedule of Assessments ([Table 5](#) and [Table 6](#)) and as clinically indicated. If signs/symptoms indicating liver injury occur, instructions contained in the table for dose reduction and interruptions of the protocol should be followed (see [Table 1](#)). Appropriate supportive care should be provided together with close monitoring. If hepatic failure occurs the study drug must be discontinued.

#### 8.4.1.1.6 MANAGEMENT OF THROMBOEMBOLIC EVENTS

Subjects should be advised to pay attention to symptoms suggestive of venous thromboembolic events which include acute onset of shortness of breath, dyspnea, chest pain, cough, hemoptysis, tachypnea, tachycardia, cyanosis, deep vein thrombosis signs including lower-extremity swelling, redness and warmth to touch or tenderness. In case any of these symptoms appear, subjects should be instructed to report such symptoms promptly to the treating physician. If a thromboembolic event is confirmed, instructions contained in the table for dose reduction and interruptions of the protocol should be followed (see [Table 1](#)). Appropriate supportive care should be provided together with close monitoring. If a subject experiences a Grade 3 or a life-threatening (Grade 4) thromboembolic reaction, including pulmonary embolism, study drug must be discontinued.

Arterial thromboembolic events (eg, new onset, worsening, or unstable angina, myocardial infarction, transient ischemic attack, and cerebrovascular accident) of any grade require study drug discontinuation.

#### 8.4.1.1.7 MANAGEMENT OF HYPOCALCEMIA

Serum calcium should be monitored monthly per the Schedule of Assessments ([Table 5](#) and [Table 6](#)). Corrected serum calcium should be used to assess the grade of hypocalcemia per CTCAE v5.0, using the following formula:

$$\text{Corrected calcium} = ([4 - \text{serum albumin in g/dL}] \times 0.8 + \text{serum calcium})$$

The formula is not applicable when serum albumin concentration is normal (>4 g/dL); in such situations, the total (uncorrected) serum calcium should be used instead.

Hypocalcemia should be treated per institutional guidelines (eg, using appropriate calcium, magnesium, and Vitamin D supplementation) until resolution.

#### 8.4.1.1.8 MANAGEMENT OF GASTROINTESTINAL SYMPTOMS AND ACUTE ABDOMINAL PAIN

Initial management of acute abdominal pain in these study subjects should be focused on treating the underlying cause where possible, ensuring appropriate hydration/rehydration, and symptomatic pain improvement consistent with subject's age and in accordance to local and

institutional standards of care. Appropriate supportive care should be provided together with close monitoring.

For adverse events of abdominal pain believed related to lenvatinib or more specific adverse events believed related to lenvatinib that result in the symptom of abdominal pain, follow instructions contained in [Table 1](#) regarding study treatment dose reduction and interruption. For Grade 4 adverse events that result in abdominal pain, study drug must be discontinued.

Gastrointestinal symptoms including diarrhea should be managed by providing symptomatic treatment. If the symptoms persist (eg, diarrhea for more than 10 days), dose modification guidelines should be followed as per [Table 1](#). Gastrointestinal symptoms should be monitored closely and evaluated using CT, contrast-enhanced MRI, ultrasound, or other diagnostic imaging if clinically indicated, at the investigator's discretion.

Lenvatinib should be discontinued in any subject who develops gastrointestinal perforation of any grade or Grade  $\geq 4$  fistula.

#### 8.4.1.1.9 MANAGEMENT OF HEMORRHAGE

Dose modification guidelines as per [Table 1](#) for lenvatinib related adverse events should be followed for the management of hemorrhage. Either resume lenvatinib at a reduced dose or discontinue lenvatinib, depending on the severity and persistence of hemorrhage.

#### 8.4.1.2 Management of Ifosfamide-Etoposide Associated Toxicity

Blood counts should be closely monitored during and prior to the next cycle of chemotherapy. Chemotherapy-associated myelosuppression should be managed by granulocyte-colony stimulating factor (G-CSF). It is recommended that pegylated G-CSF or G-CSF be administered at least 24 to 72 hours after completion of ifosfamide-etoposide chemotherapy; use of G-CSF is recommended until white blood cell (WBC) counts are  $\geq 1 \times 10^9/L$ . Guidelines for dose modification for ifosfamide and etoposide associated toxicities are provided in the [Table 2](#) below.

Details of ifosfamide and etoposide dose interruption and reduction as well as management of toxicity can be found in the Summary of Product Characteristics (SmPC), and may be followed as per local and institutional guidelines. The SmPC will be provided to the study sites in the Investigator and Pharmacy files in the relevant local language. For additional information investigators may refer to the SmPC or Euramos-1 protocol (ISRCTN67613327 EudraCT no. 2004-000242-20).

**Table 2 Criteria for Dose Modification of Chemotherapy Dose**

Toxicity	Grade	Action
Neutropenia	Grade 4	Monitor ANC counts every 3 days until resolved to <Grade 3
Febrile neutropenia	Grade 4	Reduce the next dose of ifosfamide and etoposide by 20%
Mucositis	Repeated grade 3 or Grade 4	Reduce etoposide by 20%
Renal Toxicity	Serum creatinine is 1.5 – 3 × ULN maximum serum creatinine for age and gender	Interrupt ifosfamide and etoposide for 1 week
Hematuria	>50 RBC/ high power field (hpf)	Interrupt ifosfamide for 1 week
Neurological Toxicity	≥ Grade 2	Interrupt and reduce ifosfamide and etoposide each by 20% of the previous dose. After 2 dose reductions, subject must discontinue the chemotherapy drugs, but if benefiting, can continue on single-agent lenvatinib at the investigator's discretion

ANC = absolute neutrophil count, RBC = red blood cell, ULN = upper limit normal.

#### 8.4.2 Identity of Investigational Product(s)

Lenvatinib will be supplied by the sponsor in labeled containers. The sponsor will package lenvatinib as open-label supplies. Lenvatinib will be provided to the sites as #4 size hydroxypropyl methylcellulose (HPMC) capsules in 3 strengths differentiated by color (iron oxide red and iron oxide yellow); 1-mg capsule (yellowish red cap and white body, containing 1 mg E7080 anhydrous free base), 4 mg capsule (yellowish-red cap and body, containing 4 mg E7080 anhydrous free base); and 10 mg capsule (yellowish-red cap with yellow body, containing 10 mg E7080 anhydrous free base). Excipients of the E7080 formulation will be calcium carbonate, mannitol, microcrystalline cellulose, hydroxypropylcellulose, low-substituted hydroxypropylcellulose, talc, hypromellose, titanium dioxide, iron oxide yellow, and iron oxide red. Lenvatinib capsules may be suspended in water or apple juice for children unable to swallow capsules. [Appendix 4](#) provides instructions for the preparation of the lenvatinib suspension.

##### 8.4.2.1 Chemical Name of E7080

- Test drug code: E7080
- Generic name: lenvatinib
- Chemical name: 4-[3-Chloro-4-(*N*-cyclopropylureido)phenoxy]-7-methoxyquinoine-6-carboxamide methanesulfonate
- Molecular formula: C21H19ClN4O4•CH4O3S
- Molecular weight: 522.96

#### 8.4.2.2 Comparator Drug

##### Cytotoxic Chemotherapy: Ifosfamide and Etoposide

The cytotoxic chemotherapy drugs (used in combination with lenvatinib) in this study will be ifosfamide and etoposide. These chemotherapy drugs will be provided by the sponsor or sourced by the clinical sites. The administration procedure should follow the approved prescribing information in each country/region. The chemotherapy regimen schedule and dosing details are provided below.

The chemotherapy regimen schedule will consist of ifosfamide 3000 mg/m^2/day IV infusion over 30 minutes for 3 consecutive days (Day 1 to Day 3 of each cycle) and etoposide 100 mg/m^2/day IV infusion for 3 consecutive days (Day 1 to Day 3 of each cycle). Chemotherapy administration should be accompanied by vigorous hydration and administration of mesna according to the institutional guidelines. Each chemotherapy cycle will be 21 days for a total of 5 cycles.

Pegylated G-CSF or G-CSF will be administered at least 24 to 72 hours after completion of ifosfamide-etoposide chemotherapy until WBC counts are  $\geq 1 \times 10^9/L$  or at the investigator's discretion.

Anti-emetic or any other prophylaxis should be administered in accordance with institutional guidelines.

#### 8.4.2.3 Labeling for Study Drug

Lenvatinib and the combination chemotherapy drugs, ifosfamide and etoposide, where supplied by the sponsor will be labeled in accordance with text that is in full regulatory compliance with each participating country and is translated into the required language(s) for each of those countries.

The following information will be provided (but not limited to):

- For clinical trial use only
- Name and address of the sponsor
- Chemical name / drug identifier
- Lot number/Batch number
- Storage conditions, expiration date if necessary

